#### Slit Lamp

For each considered evaluation type (Lids, Cornea, Conjunctiva, Iris, Anterior chamber, Aqueous flare, Aqueous inflammatory cells, Lens) and eye side, the number & percentage of subjects with and without abnormality (normal, insignificant, clinically significant) will be provided by timepoint and treatment arm. Further, shift tables will be generated for each eye, evaluation type, and treatment arm by time point separately. In addition, for each slit lamp evaluation, shift tables will be generated to present the worst post-baseline changes compared to baseline by treatment arm and eye side. A listing of subjects with any abnormality will be provided. Subjects with abnormalities recorded in free text of "Abnormalities" section of the "Ophthalmic Examinations - Slit Lamp Exam" CRF for the following eye parts - lids/lashes, cornea, conjunctiva, iris & anterior chamber will be coded using MedDRA (version 26.0) and these coded ocular terms will be summarized using frequency counts and percentages by timepoints. Further, subjects with abnormalities recorded in free text of "Abnormalities" section of the "Ophthalmic Examinations - Slit Lamp Exam" CRF abnormalities for the following eye parts - aqueous flare, aqueous inflammatory cells, lens will be reported as recorded in CRF by frequency and percentages. A listing for the MedDRA coded ocular terms will also be presented.

Novartis	Confidential	Page 25 of 36
SAP Amendment 1		Study No. CICL670F2203

#### **Lens Opacification**

The Lens opacification will be measured by the LOCSIII with categories as mentioned in the CRF. These assessments will be summarized using shift tables – the changes in LOCSIII grade will be presented for each eye, evaluation type (Nuclear Color, Nuclear Opalescence, Cortical, Posterior Subcapsular) and treatment arm by time point. Additionally, the worst change in grade compared to baseline for each eye, evaluation type, and treatment arm will also be presented using shift tables. Swimmer plots will be generated to show the categories of LOCSIII at baseline versus scheduled visits for each of the evaluation types by treatment arm and eye side. The treatment duration will also be displayed on the plot. A listing of subjects will be provided.

#### Fundus Oculi

For each considered evaluation type (Peripheral Retina, Macula, Optic Nerve, & Vitreous Hemorrhage) and eye side, the number & percentage of subjects with and without abnormality will be provided by timepoint, eye side and treatment arm. In addition, shift table will be generated to present the worst post-baseline changes compared to baseline by eye side and treatment arm. A listing of subjects with any abnormality will be provided. Subjects with abnormalities recorded in free text of "Other Findings (Abnormalities)" section of the "Dilated Fundus Examination" CRF will be coded using MedDRA (version 26.0) and these coded ocular terms will be summarized by timepoints using frequency counts and percentages. A listing for the MedDRA coded ocular terms will also be presented.

#### **Color Fundus Photography**

The Color Fundus Photography Assessment will be conducted by a central vendor though photographs. For each considered evaluation type and eye side, the number & percentage of subjects with and without abnormality will be provided by timepoint and treatment arm. A listing of subjects will be provided; additionally, listings for the findings, general comments and confidence score comments will be presented.

#### 2.6.3 Adverse Events (AEs)

Adverse Event summaries will include all AEs occurring during on treatment period (see Section 2.1.1).

In AE summaries, the primary system organ class will be presented alphabetically, and the preferred terms will be sorted within primary SOC in descending frequency. The sort order for the preferred term will be based on their frequency in the Deferasirox FCT arm.

The following adverse event summaries will be produced by treatment arm. A subject with multiple occurrences of an AE will be counted only once in the respective AE category.

- Adverse events, regardless of study treatment relationship by primary system organ class, preferred term, and severity (mild, moderate & severe)
- Adverse events with suspected study treatment relationship by primary system organ class, preferred term, and severity

Novartis	Confidential	Page 26 of 36
SAP Amendment 1		Study No. CICL670F2203

- Serious adverse events, regardless of study treatment relationship, by primary system organ class, preferred term, and severity
- Serious adverse events, with suspected study treatment relationship, by primary system organ class, preferred term, and severity
- Adverse events leading to study treatment discontinuation, regardless of study drug relationship, by primary system organ class, preferred term, and severity
- Adverse events requiring dose adjustment or study treatment interruption, regardless of study treatment relationship, by primary system organ class, preferred term, and severity
- Adverse events requiring additional therapy, regardless of study treatment relationship, by primary system organ class, preferred term, and severity
- Deaths (all and on-treatment) by primary system organ class and preferred term

To assess the secondary safety objective on evaluation of safety and tolerability of deferasirox FCT in subjects who interrupt due to SF  $\leq 100 \ \mu$ g/L and re-initiate therapy when  $\geq 300 \ \mu$ g/, the number (%) of subjects who met the criteria of interruption due to SF  $\leq 100 \ \mu$ g/L and re-initiation of therapy when  $\geq 300 \ \mu$ g and interruption due to SF  $\leq 100 \ \mu$ g/L will be summarized respectively.

The summaries from above (barring the last two) will be repeated for subjects who interrupted deferasirox FCT at least once due to  $SF \le 100 \ \mu g/L$  and re-initiated  $\ge 300 \ \mu g/L$  will be tabulated. If less than 10 subjects meet the above criteria, only listings will be generated.

AEs will be summarized by presenting the number and percentage of subjects having at least one AE, and having at least one AE by system organ class and preferred, severity and relation to study treatment by arm. A subject with multiple occurrences of an AE will be counted only once in the worst AE category (if it occurs in multiple categories).

An overall summary of type of AEs (e.g. serious, leading to study drug discontinuation, requiring dose adjustment or/and interruption) will be presented by severity and treatment arm. Additionally, for those with dose interruptions (FCT re-initiation), the overall summary for the AEs will generated as described above.

All AEs will be listed. Any information collected (e.g. regardless to study drug, action taken etc.) will be listed as well as the duration of the AE.

The listings of all deaths, serious adverse events, adverse events leading to study drug discontinuation, and adverse events requiring dose adjustment or interruption will also be provided.

Summaries of COVID related adverse events as defined in the eCRS will be provided by treatment arm. A listing of COVID related AEs and deaths will also be generated.

A listing of all grouping levels down to the MedDRA preferred terms used to define each AESI will be generated.

#### 2.6.4 Deaths

Separate summaries for on-treatment and all deaths (including post-treatment death) will be produced by treatment arm, system organ class and preferred term (primary reason of death).

All deaths will be listed, pre-treatment (if any) and post treatment deaths will be flagged.

#### 2.6.5 Adverse Events of Special Interest (AESI)

An adverse event of special interest is a grouping of adverse events that are of scientific and medical concern specific to compound ICL670. These groupings are defined in the eCRS using MedDRA terms, SMQs, HGLTs (high level group terms), HLT and PTs. Customized SMQs (NMQ) may also be used. A NMQ is a customized group of search terms which defines a medical concept for which there is no official SMQ available or the available SMQ does not completely fit the need. It may include a combination of single terms and/or an existing SMQ, narrow or broad. The latest version of the eCRS available at the time of the analysis will be used.

For each specified AESI, number and percentage of subjects with at least one event of the AESI occurring during on treatment period will be summarized.

Summaries of these AESIs will be provided for each of the two treatment arms by grouping and preferred term -

- AESIs, regardless of study treatment relationship
- AESIs, with suspected study treatment relationship
- Serious AESIs regardless of study treatment relationship
- Serious AESIs with suspected study treatment relationship
- AESIs leading to study treatment discontinuation
- AESIs requiring dose adjustment or study treatment interruption
- AESIs requiring additional therapy
- AESIs Outcomes Recovered or Recovering
- Deaths (all and on-treatment)

A listing of all grouping levels down to the MedDRA preferred terms used to define each AESI will be generated.

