8.1 Adverse events (AEs)

8.1.1 Definitions and reporting

An AE is defined as the appearance (or worsening of any pre-existing) of undesirable sign(s), symptom(s), or medical condition(s) that occur after ICF has been signed.

Abnormal laboratory values or test results occurring after informed consent constitute an AE if they induce clinical signs or symptoms considered clinically significant, require therapy (e.g., hematologic abnormality that requires transfusion or stem cell support), or require changes in study medication.

Onset or worsening of AEs after informed consent should be recorded in the AE eCRFs. Conditions present at the time of informed consent should be recorded in the Medical History page of the eCRF. AE monitoring should be continued for at least 30 days (or 5 half-lives, whichever is longer) following the last dose of study treatment. AEs (including lab

abnormalities that constitute AEs) should be described with a diagnosis, rather than individual underlying signs and symptoms. When a clear diagnosis cannot be identified, each sign or symptom should be reported as a separate AE.

Severity of AEs will be assessed as mild, moderate, or severe. Information about any deaths (related or not to an AE) will be collected through a Death form.

Detection of AEs should be sought by non-directed questioning of the patient during screening (after signing the ICF) and at each visit. AEs may also be volunteered by the patient during Screening, between visits, by physical examination, laboratory test, or other assessments. Each AE must be evaluated for:

- 1. Severity grade (mild, moderate, severe)
- 2. Duration (Start and end dates)
- 3. Relationship to study treatment (Reasonable possibility that AE is related: No or Yes)
- 4. Action taken with respect to study drug (None, Dose adjusted, Temporarily interrupted, Permanently discontinued, Unknown, or Not applicable)
- 5. Concomitant medication or therapy given (No concomitant medication/non-drug therapy; if Yes, provide the concomitant medication/non-drug therapy)
- 6. Seriousness criteria was met or not for an AE, as defined in Section 8.2.1
- 7. Outcome (Not recovered/not resolved, Recovered/resolved, Recovering/resolving, Recovered/resolved with sequelae, Fatal, Unknown)

For SAEs only, if there is improvement to a lower grade or worsening in toxicity, a new second entry with the start date should be reported in the eCRF.

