#### 2.5.2 Statistical Hypothesis, Model, and Method of Analysis

To characterize long-term ocular safety, the incidence of treatment-emergent ocular AEs (new or worsening from baseline) will be summarized (along with two-sided exact binomial 95% CIs [Clopper and Pearson, 1934]) by preferred term, overall and by severity, type of AE (e.g. serious, leading to study drug discontinuation, requiring dose adjustment or/and interruption), and relation to study treatment.

Treatment-emergent AEs are defined as AEs started during on-treatment period: from the day of the first dose of study medication or the first phlebotomy to 30 days after the last dose of study medication or last phlebotomy.

All ocular AEs included under "Lens disorders, retinal disorders and optic neuritis" Adverse Event of Special Interest (AESI, listed in the compound case retrieval strategy) will be reported.

Novartis	Confidential	Page 22 of 36
SAP Amendment 1		Study No. CICL670F2203

The above analysis will also be repeated for the overall period (on-treatment & post-treatment).

The analyses will be descriptive. No formal hypothesis testing is planned for this key secondary objective.

A listing of Ocular AEs will also be generated, and post-treatment events will be flagged.

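### SAP 2.6.5 tabulates AESI outcome only as recovered or recovering, so no planned table gives the by-arm count of unfavourable outcomes, including for the key secondary ocular AESI

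*SAP*

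**What the plan says.** Protocol 8.1.1 requires each adverse event to be evaluated for, among other items, "Outcome (Not recovered/not resolved, Recovered/resolved, Recovering/resolving, Recovered/resolved with sequelae, Fatal, Unknown". That is six categories.

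SAP 2.6.5 sets the counting unit for AESIs: "number and percentage of subjects with at least one event of the AESI occurring during on treatment period will be summarized". It then lists the summaries to be produced by grouping, preferred term and arm. These start with "AESIs, regardless of study treatment relationship" and go on to related, serious, discontinuation, dose-adjustment and additional-therapy tables. Outcome appears in two places only: "AESIs Outcomes Recovered or Recovering" and "Deaths (all and on-treatment".

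SAP 2.5.1 defines the key secondary endpoint through one AESI grouping: lens disorders, retinal disorders and optic neuritis. SAP 2.5.2 breaks these events down by preferred term, severity, type and relation to treatment, on-treatment and again for the overall period. Outcome is not one of the breakdowns.

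SAP 2.6.3 has a rule for repeated events in the general adverse event summaries: "A subject with multiple occurrences of an AE will be counted only once in the worst AE category (if it occurs in multiple categories". It does not mention outcome, and 2.6.5 does not repeat it. On listings, 2.6.3 says: "Any information collected (e.g. regardless to study drug, action taken etc.) will be listed as well as the duration of the AE".

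**The concern.** The study is run partly to meet a post-marketing requirement on ocular safety. For a lens, retinal or optic nerve event, whether it resolves is a natural question straight after whether it occurred. The protocol collects the answer and requires events to be followed until they resolve or are judged permanent. The only planned tabulation of that answer, apart from deaths, keeps the favourable categories.

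The stake is what a reader of the tables can learn. They will see by arm how many subjects had an AESI and how many had one that recovered or was recovering. They will not see by arm how many had one that did not recover.

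**Working it through.** No figure in the plan needs reproducing. The check sets the collected categories against the planned tables.

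| Outcome collected (Protocol 8.1.1) | Counted by outcome and arm in |
|---|---|
| Recovered | SAP 2.6.5, the recovered-or-recovering row |
| Recovering | Same row, not separable from recovered |
| Recovered with sequelae | Not stated: either inside that row or in no table |
| Not recovered | No table |
| Unknown | No table |
| Fatal | SAP 2.6.5, deaths summary |

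The general adverse event tables in SAP 2.6.3 and the ocular tables in 2.5.2 add nothing here, because neither is split by outcome. The 2.6.5 summaries cover on-treatment events, so the overall-period ocular analysis in 2.5.2 has no non-fatal outcome row at all.

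**Can the missing count be obtained by subtraction?** Take an example with invented counts. In one grouping and arm, 10 subjects have an AESI: 4 have only resolved events, 3 have one resolved and one unresolved, and 3 have only unresolved events (4 + 3 + 3 = 10). The number with at least one unresolved event is 3 + 3 = 6.

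- Counting subjects with at least one recovered or recovering event, the row shows 4 + 3 = 7, and subtraction gives 10 − 7 = 3.
- Classifying each subject by worst outcome, the row shows 4, and subtraction gives 10 − 4 = 6.

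The same data give 3 or 6. The 2.6.5 counting unit points to the first reading and the 2.6.3 worst-category rule would suggest the second. The SAP does not say which applies to outcome.

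Even with one event per subject the difference is not the number unresolved. It pools not recovered, unknown, fatal and possibly sequelae.

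**Denominator.** SAP 2.1 (general analysis conventions) takes percentages over all subjects in the arm. The row's percentage is therefore not a recovery proportion among affected subjects.

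**The case against.** Several points on the other side are sound.

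- **The events are not lost.** A reader might infer that unresolved AESIs drop out of the tables. They do not. Each on-treatment AESI is counted in the overall AESI table, and in the related, serious, discontinuation and other tables where it qualifies. Only the count by outcome is missing.
- **Outcomes are listed.** The adverse event listing carries all collected information, ocular events have their own listing, and SAP 5.1.2 shows continuing events as ongoing. With few events a reader could count from it, but a listing gives no planned count by arm.
- **Preferred-term rows limit the masking.** If a subject's resolved and unresolved events fall under different terms, subtraction within each term shows one without recovery. Masking within a term needs two events of the same term with different outcomes. Term-level differences still pool several outcomes, and they cannot be summed to subjects per grouping because one subject can appear under several terms.
- **Events may be rare.** Protocol 2.6 cites under 1% for lens, pressure and retinal disturbances, so fewer than 100 × 0.01 = 1 subject expected among 100 on deferasirox. Scheduled eye examinations about every 6 months may find more. Rarity makes mixed-outcome subjects less likely, but it does not supply the missing categories.
- **Persistence of ocular findings is covered elsewhere.** SAP 2.6.2 plans visit-by-visit shift tables for acuity, pressure, slit lamp and lens opacity, worst-change shifts including fundus, swimmer plots for acuity and lens opacity, and central photography by time point. A reader might infer that the plan conceals persistence; these analyses show otherwise. They report examination findings, however, not the outcome of a reported event.
- **The protocol endpoint is met.** The key secondary endpoint is incidence by severity, type and relation, and 2.5.2 delivers it.

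A reader might also extend the point to renal and hepatic events. The documents name only the ocular grouping; the others are defined in the case retrieval sheet, which is not part of the protocol or SAP.

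**Conclusion.** The point holds as a minor reporting gap. Of six collected outcomes, two are merged into one favourable row, fatal has its own table, two (not recovered and unknown) have no count by arm, and the place of sequelae is unstated. The ocular AESI is affected like any other.

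A subject with mixed outcomes in a grouping can be counted as recovered. It would go too far to say that such a subject is shown only as recovered: the same subject is in the overall AESI table, and the SAP states no mixed-outcome rule from which the classification would follow for certain.

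No endpoint estimate is biased and nothing departs from the protocol. How often subtraction would mislead cannot be sized, because the documents give neither the number of events per affected subject nor their outcomes. The conclusion rests on reading the 2.6.5 list as the complete set of AESI summaries.

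**What to change.** In SAP 2.6.5, replace the recovered-or-recovering bullet with a summary of AESIs by each of the six collected outcomes, by grouping, preferred term and arm. Give event counts for each outcome, and number and percentage of subjects classified by worst outcome. State the ranking in the SAP. The sponsor should fix it before database lock, including where unknown and recovered with sequelae stand.

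At minimum, do this for the ocular AESI in SAP 2.5.2, for both the on-treatment and the overall period.

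The cost is one SAP bullet and one reprogrammed table, with no new data because outcome is already on the adverse event eCRF. The downside is a longer table that looks less favourable.

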#### 2.6.6 Disclosure Related Outputs

For the legal requirements of ClinicalTrials.gov and EudraCT, two required tables will be produced for the Safety Set at the time of the final CSR:

- Non-serious adverse events with an incidence greater than 5%
- Serious adverse events (SAE) and SAE suspected to be related to study treatment will be provided by system organ class and preferred term. The number of deaths resulting from SAEs suspected to be related to study treatment and SAEs irrespective will also be provided.

If for a same subject, several consecutive AEs (irrespective of study treatment causality, seriousness and severity) occurred with the same SOC and PT:

Novartis	Confidential	Page 28 of 36
SAP Amendment 1		Study No. CICL670F2203

- A single occurrence will be counted if there is  $\leq 1$  day gap between the end date of the preceding AE and the start date of the consecutive AE
- More than one occurrence will be counted if there is > 1 day gap between the end date of the preceding AE and the start date of the consecutive AE

For occurrence, the presence of at least one SAE / SAE suspected to be related to study treatment / non-SAE has to be checked in a block e.g., among AEs in  $a \le 1$  day gap block, if at least one SAE is occurring, then one occurrence is calculated for that SAE.

#### 2.6.7 Laboratory Data

On analyzing laboratory, data from all sources (central and local laboratories) will be combined. The summaries will include all assessments available for the lab parameter collected no later than 30 days after the last study treatment administration date (see Section 2.1.1).

The following summaries will be produced for hematology, urinary, and biochemistry laboratory data (by laboratory parameter and treatment):

- Descriptive Statistics for lab results and change by from baseline time point and treatment arm
- Shift tables using notable/extended ranges to compare baseline to the worst on-treatment value for key lab parameters (see Table 2-1)
- Shift tables using the low/normal/high/(low and high) classification to compare baseline to the worst on-treatment value.
- Trends of key lab parameter values over time (baseline and selected on-treatment timepoints) will be displayed via boxplots based on time windows and corresponding tables displaying the statistics used for the box plots by the selected time points.

The following listings will be produced for the laboratory data:

- Listings of all laboratory data, with classification relative to the laboratory normal range.
- Listing of all lab abnormalities based on notable/extended ranges

Parameter	Criteria
Absolute neutrophils	$< 1.5 \times 10^{9}$ /L (extended range $< 0.5 \times 10^{9}$ /L)
Platelets	$< 100 \times 10^{9}$ /L (extended range $< 50 \times 10^{9}$ /L)
Hemoglobin	< 100 g/L
ALT and AST	$> 5 \times$ ULN and $> 2 \times$ baseline (extended range $> 10 \times$ ULN and $> 2 \times$ baseline)
Total bilirubin	> 2 x ULN
Serum creatinine	> 33% increase from baseline and > ULN at 2 consecutive measurements at least 7 days apart
Creatinine clearance	< 60 mL/min at 2 consecutive measurements at least 7 days apart (extended range < 40 mL/min at least 7 days apart)
Urinary protein/creatinine ratio*	$\geq$ 1.0 mg/mg at 2 consecutive measurements at least 7 days apart

 Table 2-1 Definition of notable/extended ranges for key safety laboratory parameters

Novartis	Confidential	Page 29 of 36
SAP Amendment 1		Study No. CICL670F2203

\* If the unit of the parameter (Urinary protein/creatinine ratio) is in mg/mmol then will have to use a conversion factor as 0.00885 to convert into mg/mg unit for further derivation.

For all analyses, creatinine clearance will be re-derived using the Cockcroft-Gault equation described in Section 5.2.1.

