Increased creatinine ≥ 33% from baseline (average of 2 samples) resulting in creatinine > ULN x 2 consecutive samples (at least 2 weeks apart)	Decrease by 7 mg/kg/day or interrupt if already at 7 mg/kg/day or lower.	
If dose is decreased, but increasing creatinine > ULN	Interrupt treatment.	
After interruption, if creatinine returns to within normal limits on 2 consecutive visits.	Resume 50% of the most recent dose prior to interruption. If after another 4 weeks, creatinine remains stable, resume 100% dose (adjust for weight if needed).	
Creatinine clearance > 40 and < 60 mL/min	Caution in patients if there are additional risk factors that may impair renal function, such as concomitant medications, dehydration, or severe infection.	

Dece medifications for ICL 67052202	
Creatinine clearance < 40 mL/min	Deferasirox must be discontinued.
or increased serum creatinine > 2x age-appropriate ULN	
Urine protein/creatinine ratio	
Any proteinuria	If new or worsening pre-existing proteinuria (assessed by dipstick), collect a urine sample for assessment by the central/local laboratory.
	In case of a single increase of the urinary protein/creatinine ratio, repeat the assessment at the next visit.
> 0.5 urine protein/ creatinine ratio (mg/mg) in two consecutive non-first void urine samples (a minimum of 48h apart), if all other causes of proteinuria have been	Decrease deferasirox by 50%. If UPCR resolves (< 0.5mg/mg) at the next study visit, resume 100% dose.
excluded.	
> 1.0 (mg/mg) in two consecutive non-first void urine	Interrupt deferasirox FCT.
samples (a minimum of 48h apart)	If the increased UPCR resolves (< 0.5 mg/mg) at the next study visit, resume dose at 50% of the last dose. If UPCR remains within normal limits after 4 weeks at the 50% reduced dose, resume study medication at 100% of the last dose.
Persistent proteinuria	If proteinuria persists, discontinue study treatment if the investigator believes it is in the best interest of the patient.
	Novartis may be contacted by the investigator to discuss dosing options.
	Dose adjustment must be based on central/local laboratory results.
Investigations (Hepatic)	
Isolated direct (conjugated) Bilirubin elevation	
> ULN – 1.5 x ULN	Maintain dose
> 1.5 - 3.0 x ULN	Interrupt dosing. Monitor LFTs ^a weekly or more frequently if clinically indicated until resolved to \leq 1.5 x ULN: If resolved \leq 14 days, then maintain dose.
	If resolved > 14 days, then \downarrow 1 dose level (3.5 mg/kg/day FCT)

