10.5.3.3 Laboratory abnormalities

All laboratory values will be converted into SI units and reported by the severity grade, using low/normal/high classifications based on laboratory normal ranges, and by notable/extended ranges for selected parameters (see Table 10-1).

Parameter	Criteria
Absolute neutrophils	< 1.5×10 ⁹ /L (extended range < 0.5×10 ⁹ /L)
Platelets	< 100×10 ⁹ /L (extended range < 50×10 ⁹ /L)
Hemoglobin	< 100 g/L
ALT and AST	> 5× ULN and > 2× baseline (extended range > 10× ULN and > 2× baseline)
Total bilirubin	> 2 mg/dL
Serum creatinine	> 33% increase from baseline and > ULN at 2 consecutive measurements at least 7 days apart
Creatinine clearance	< 60 mL/min at 2 consecutive measurements at least 7 days apart (extended range < 40 mL/min)
Urinary protein/creatinine ratio	≥ 1.0 mg/mg at 2 consecutive measurements at least 7 days apart

 Table 10-1
 Criteria for clinically notable and extended notable laboratory ranges

The following summaries will be generated separately for hematology, biochemistry, and urinary laboratory tests:

• Shift tables using normal/notable/extended ranges to compare baseline to the worst ontreatment value • Listing of all laboratory data with values flagged to show the corresponding normal/notable/extended ranges (see Table 10-1 above).

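### SAP Table 2-1 adds a 7-day repeat to the creatinine-clearance range below 40 mL/min that protocol Table 10-1 does not have, so the shift table can undercount that range on deferasirox

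*SAP*

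**What the plan says.** Three places bear on creatinine clearance below 40 mL/min.

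- **SAP Table 2-1 (section 2.6.7).** The creatinine-clearance row reads "< 60 mL/min at 2 consecutive measurements at least 7 days apart (extended range < 40 mL/min at least 7 days apart". The notable range comes first, and the bracket that follows gives the extended range. These ranges feed a shift table from baseline to the worst on-treatment value and a listing of abnormalities.
- **Protocol Table 10-1 (section 10.5.3.3).** The notable range is the same, but the bracket reads only "extended range < 40 mL/min", with no interval.
- **Protocol Table 6-2 (section 6.3.1).** The trigger is "Creatinine clearance < 40 mL/min" (or a serum creatinine criterion in the same row), and the action is "Deferasirox must be discontinued". This row states no repeat.

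The SAP's document history notes that Amendment 1 redefined the notable range for creatinine clearance. SAP section 4, which lists changes to the protocol's analyses, names only COVID-19 items and the ocular windows.

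**The concern.** The SAP has added a confirmation condition to the most severe renal category, and that condition interacts badly with the trial's own stopping rule. If drug is stopped on a value below 40 mL/min, the second value, 7 or more days later, will usually be taken off drug. The category then records whether the low clearance persisted after withdrawal, when the protocol's definition records whether it occurred on treatment.

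The effect is not the same in both arms. Table 6-2 governs deferasirox only. Phlebotomy patients have no such stop and keep their 4-weekly samples, so a low value there has more chances to be confirmed while treatment continues. A reader comparing arms in the notable/extended shift table could see fewer extended cases on deferasirox for a reason unrelated to renal safety.

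**Working it through.** The plan states no figure for this rule, so the check compares the wording and then applies the two definitions to examples.

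**Step 1. Does the SAP bracket need two values?** An interval between measurements cannot be met by one. The bracket does not restate the number of measurements or that they be consecutive, but two is the minimum. In the examples below, requiring consecutive values or accepting any two gives the same answer.

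**Step 2. Is the repeat usual for an extended range?** No. In SAP Table 2-1 the extended ranges for neutrophils, platelets and ALT/AST carry no repeat. Creatinine clearance is the only one that does.

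**Step 3. Does Table 6-2 ask for confirmation before the stop?** The row for clearance below 40 mL/min states none. Neighbouring rows say so when a repeat is wanted: serum creatinine needs two consecutive samples at least 2 weeks apart, and the urine protein/creatinine ratio needs two samples at least 48 hours apart. That the stop follows the first value is therefore the natural reading, though the row does not use that word.

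**Step 4. Apply the rules.** Seven illustrative series, assumed and not trial data: baseline 85 mL/min on day 1, one further value on day 29, then 38 mL/min on day 57, which triggers the stop. Last dose is day 60 in A to F and day 57 in G. Values count up to last dose + 30 days (SAP 2.6.7).

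| Series | Day 29 | Day 57 | Later value | Protocol extended (any < 40) | SAP extended (two < 40, ≥ 7 days) | Notable (two consecutive < 60, ≥ 7 days) |
|---|---|---|---|---|---|---|
| A | 72 | 38 | none | yes | no | no |
| B | 72 | 38 | 39, 5 days later | yes | no | no |
| C | 72 | 38 | 66, 14 days later | yes | no | no |
| D | 72 | 38 | 52, 14 days later | yes | no | yes |
| E | 55 | 38 | 62, 14 days later | yes | no | yes |
| F | 72 | 38 | 37, 14 days later | yes | yes | yes |
| G | 72 | 38 | 37 on day 95 (95 − 57 = 38 days after last dose, outside the window) | yes | no | no |

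Under the protocol wording 7 of 7 are extended; under the SAP wording 1 of 7 is. Two (D, E) fall back to notable, and four (A, B, C, G) are in neither category. The series were chosen to show the routes, so these counts are not an estimate of frequency.

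**Step 5. What would set the size?** If no other value is below 40 mL/min, the share missing from the extended category is

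share missed = 1 − P(repeat 7 or more days later, inside the window) × P(still < 40 at that repeat).

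The documents give neither probability. Taking 0.5 to 1.0 for the first and 0.25 to 0.9 for the second, purely as assumptions:

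- smallest: 1 − 1.0 × 0.9 = 0.10
- largest: 1 − 0.5 × 0.25 = 0.875, about 88%

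A range this wide shows only that the size cannot be fixed from the plan.

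**The case against.** The sponsor has several fair answers.

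- **Confirmation is reasonable and was recorded.** An isolated low value may be spurious, and the document history mentions the redefinition. This stands as a reason to show confirmed values. It does not explain why the change is missing from section 4.
- **Repeats will often exist.** A reader might infer from the empty Week 108 laboratory column in protocol Table 7-1 that no later sample is taken. The documents do not support that. Protocol section 6.3.3 requires at least 30 days of follow-up after permanent discontinuation for a laboratory abnormality that meets AE criteria, and section 8.1.2.1 requires laboratory AEs to be followed until resolved or explained. Neither names the tests, but recovery off drug is the main route to loss, and a missing repeat is the weaker one.
- **The events are reported elsewhere.** Section 8.1.2.1 makes a laboratory abnormality that forces a treatment change an AE. The SAP tabulates AEs leading to discontinuation and lists all laboratory data. It also plans a low/normal/high shift table, which would show the value if creatinine clearance has a normal range. This stands, and confines the gap to the notable/extended shift table and its listing.
- **Some patients remain notable.** Series D and E show this, so the loss from both categories is not general.

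A reader might also infer that the urine protein/creatinine ratio has the same fault, because Table 6-2 acts on two "samples (a minimum of 48h apart" while the SAP requires "1.0 mg/mg at 2 consecutive measurements at least 7 days apart". The documents do not support this as a departure: protocol Table 10-1 already has the same 7-day pair. A reporting range need not equal a dosing trigger.

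**Conclusion.** The point holds for creatinine clearance alone. SAP Table 2-1 departs from protocol Table 10-1, section 4 does not declare the departure, and with the Table 6-2 stop the notable/extended shift table and its listing can understate the most severe renal category on deferasirox. This rests on reading the SAP bracket as two values and the Table 6-2 row as needing no repeat; both are the natural readings.

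The size is unknown. It depends on how many patients reach a value below 40 mL/min, how many are resampled in time and how many recover, and the plan gives none of these.

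It would be too strong to say that the table counts only patients who stay low after drug is stopped, since two values below 40 mL/min could both precede the stop if drug was not withdrawn at once. Neither the primary endpoint nor the key secondary endpoint is affected, and no hypothesis is tested. No view is taken here on the stopping rule itself.

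**What to change.** In SAP Table 2-1, restore the protocol Table 10-1 definition: any single on-treatment creatinine clearance below 40 mL/min is extended, and the two-measurement condition applies only to the range below 60 mL/min. In the shift table, let extended take precedence over notable, so that a patient with one value below 40 mL/min is classified without a second value. Footnote each such value as confirmed or unconfirmed at 7 or more days. Since this returns to the protocol wording, it needs no entry in section 4.

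If the sponsor prefers the confirmed definition, show the single-value and confirmed counts side by side by arm, and declare and justify the change in section 4.

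Either option is one table edit and a small programming change on data already collected. The downside is that a few isolated, possibly spurious values will be counted; the footnote lets a reader set them aside.
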